who are randomized to the AHA Depression Screen, Notify & Treat arm will also complete a PHQ-8 assessment, and those with clinically significant scores (≥ 10) will be offered the option of receiving treatment for their depressive symptoms. Participants will be presented with the option of receiving medication therapy (sertraline or bupropion), Cognitive Behavioral Therapy (delivered via phone), a combination of both therapies or neither therapy. Depending on their treatment choice, they will be scheduled for their initial treatment visit, ideally within two weeks of randomization. Their PCP and/or cardiologists will also be notified if they have clinically significant scores (≥ 10) on the PHQ-8 assessment. Those randomized to No Depression Screen group will not receive the depression screen PHQ-8 at baseline.

All participants, regardless of randomization assignment, will complete the CES-D10, SF-12 health-related quality of life measure, symptoms checklist and lost productivity at enrollment and after 6-, 12-, and 18-months of study participation. All participants will also complete the PHQ-8 assessment at 18-months, with referral to treatment for those with scores ≥ 10. Participants will be contacted by telephone, or have an in-person visit scheduled, as they prefer. These administration methods have been compared in past studies and found to be equivalent. These follow-up contacts will be brief, and scheduled at the participant's convenience wherever possible.

All participants will report their health service utilization at 6-, 12- and 18-months. Additionally, all will have EMR searches of health care utilization extracted for the 18-month duration of the trial.

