4.2 Intent-to-Treat Sample

Analyses will be conducted on an intent-to-treat sample. No analyses will be conducted on a per-protocol or safety analysis sample.

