4.3. Safety Analysis Sample

Safety analyses will be conducted using the same sample as the primary efficacy sample, and an intent-to-treat analysis plan will be used.

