5.4 Sample Size Determination

The sample size of the trial was determined based on an assumed standard deviation for QALYs of 0.17.5 Additionally, based on a general health-related quality of life outcome in a prior study of management of depression for patients with cancer, we assumed a net improvement in QALYs of 0.155 over 18 months of follow-up for depressed individuals who receive depression treatment in the Screen, Notify and Treat group.6 We assumed a 0.055 gain in QALYs for all patients not directly linked to depression treatment (i.e., those in the No Screen group, the Screen & Notify group and those without elevated depressive symptoms in the Screen, Notify, and Treat group). An important consideration for this trial is that only 20% of patients randomized to the Screen. Notify and Treat group were expected to meet criteria for elevated depressive symptoms and thus, to receive depression treatment. Therefore, assuming an increase in QALYs of 0.21 (0.055 background improvement + net improvement of 0.155) over the 18-month follow-up period for the 20% of patients diagnosed and treated for depression in the Screen, Notify, and Treat group and a 0.055 improvement in QALYs for the 80% of patients in this randomization group without depression, an overall gain in QALYs of 0.086 over the 18 month follow-up period was anticipated in this randomization group (0.21 * 0.2 + 0.055 * 0.8 = 0.086). Thus, we anticipated a difference in QALYs of 0.031 (0.086 change in the Screen. Notify, and Treat group minus 0.055 in the No Screen group or Screen and Notify Group), leading to an expected effect size of 0.18 (= 0.031/0.17). With this effect size, we determined the sample size per group to be 475, which would yield 80% power for a two-sided t-test at 5% level. We chose to determine sample size based on a pairwise comparison at 80% power in the two-step procedure (described above), as a conservative approach relative to powering based on the F-test. Specifically, under the scenario where one group has higher QALY than the other two by an effect size 0.18, the F-test will yield 84% power. Adding in 5% loss to follow-up, we selected an overall sample size of n=500 in each randomization group for an overall sample size of n=1500.

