7. SAFETY/ TOLERABILITY

7.1 Primary (pre-specified) Safety Outcomes

Harms attributable to use of antidepressant medications (i.e., appetite problems, sleep problems, gastrointestinal upset, and bleeding) will be assessed through patient interview. Group differences in the prevalence of these potential adverse effects will be compared using chi-squared tests.

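### SAP 7.1 asks about harms of antidepressant use but tests them only across whole arms, where any excess in drug-takers is cut to about one fifth or less and no interval is planned

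*SAP*

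**What the plan says.** SAP 7.1 defines the primary safety outcomes by their cause: "Harms attributable to use of antidepressant medications (i.e., appetite problems, sleep problems, gastrointestinal upset, and bleeding) will be assessed through patient interview". The analysis is one sentence: "Group differences in the prevalence of these potential adverse effects will be compared using chi-squared tests". It states no time point, baseline adjustment, effect measure, confidence interval or expected rate.

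On the population, SAP 4.3 says "Safety analyses will be conducted using the same sample as the primary efficacy sample", by intention to treat, and SAP 4.2 says "No analyses will be conducted on a per-protocol or safety analysis sample". Harms are therefore compared over everyone randomised.

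On exposure, SAP 5.4 says "only 20% of patients randomized to the Screen. Notify and Treat group were expected to meet criteria for elevated depressive symptoms". Under Protocol, Interventions, those who qualify (PHQ-8 of 10 or more) may choose medication, telephone CBT, "a combination of both therapies or neither therapy".

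On data, Protocol, Interventions says "All participants, regardless of randomization assignment, will complete the CES-D10, SF-12 health-related quality of life measure, symptoms checklist and lost productivity at enrollment", with the same measures repeated at 6, 12 and 18 months. Under Implementation, baseline assessments come before randomisation, and the PHQ-8 is given after it, in the two screened arms only.

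**The concern.** The question concerns people who take an antidepressant, while the test averages over an arm in which about four in five are not expected to be offered one by the study. SAP 5.4 allows for exactly this dilution when it sizes the trial for QALYs. SAP 7.1 makes no matching allowance for harms and plans no interval that would show how much harm the data leave open.

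At stake is how informative the prespecified primary safety analysis can be. A real excess of side effects in treated participants could leave a whole-arm p-value well above 0.05, and the reader would have nothing in the plan's output to show that the result was also compatible with a large excess. Appetite and sleep problems can also be symptoms of depression, so benefit and harm may offset each other in an unadjusted prevalence.

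**Working it through.** **1. The plan's own figure.** Dilution for efficacy: 0.155 × 0.20 = 0.031 QALY. With SD 0.17, two-sided 5% and 80% power, n = 2 × (1.960 + 0.842)² × 0.17² / 0.031² = 472.1, so 473 per arm against 475 stated. Then 475 / 0.95 = 500. The sample size reproduces. The SAP gives no power figure for harms.

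**2. Inputs for harms.**
- From the documents: 500 randomised and 475 evaluable per arm; 20% expected to qualify, so 0.20 × 475 = 95 screen-positives per screened arm.
- Assumed, because the documents give none: background prevalence 2% to 40%; a 15-point excess in drug-takers; uptake of drug among those who qualify 100% or 50%; two-sided 5%; no excess drug use in the comparator arm; the same background in screen-positives as in the whole arm.

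**3. Dilution.** Whole-arm shift = 0.20 × uptake × 15 points = 3.0 points at full uptake and 1.5 points at half.

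**4. Pairwise power.** Power = Φ{[d − 1.96 √(2p̄(1−p̄)/n)] / √[(p₀(1−p₀) + p₁(1−p₁))/n]}, where d = p₁ − p₀ and p̄ is their mean.
- Whole arm, 20% background, full uptake, n = 500: p₁ = 0.23, p̄ = 0.215; (0.0300 − 0.0509)/0.0260 = −0.806; power 21%.
- Screen-positives, same case, n = 95: p₁ = 0.35, p̄ = 0.275; (0.1500 − 0.1270)/0.0639 = 0.360; power 64%.

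Power (%) over the assumed range:

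| Background | Whole arm, n = 500, full uptake | Same, n = 475 | Screen-positives, n = 95, full uptake | Whole arm, n = 500, half uptake | Same, n = 475 | Screen-positives, n = 95, half uptake |
|---|---|---|---|---|---|---|
| 2% | 73.3 | 71.1 | 94.7 | 30.5 | 29.2 | 60.4 |
| 5% | 48.6 | 46.6 | 88.4 | 17.3 | 16.7 | 44.8 |
| 10% | 31.8 | 30.5 | 78.1 | 11.6 | 11.2 | 32.2 |
| 20% | 21.0 | 20.2 | 64.1 | 8.5 | 8.2 | 22.7 |
| 30% | 17.4 | 16.7 | 57.0 | 7.4 | 7.2 | 19.2 |
| 40% | 15.9 | 15.3 | 54.4 | 7.0 | 6.8 | 17.9 |

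SAP 7.1 does not say whether the chi-squared test is pairwise or over three groups. A three-group test with 475 per arm gives about 15% to 81% at full uptake and 7% to 31% at half, so the picture is the same except that it does better at 2% background.

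**5. Excess needed for 80% whole-arm power (pairwise, n = 475, full uptake).** The whole-arm difference must be 3.4 points at 2% background, 7.7 at 20% and 9.0 at 40%. Divided by 0.20, that is an excess in takers of about 17, 39 and 45 points. At half uptake these double.

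**6. What a null leaves open.** At 20% background and 475 per arm, an observed difference of zero has a 95% half-width of 1.96 × √(2 × 0.20 × 0.80 / 475) = 0.051, about 5 points. The upper limit corresponds to 0.051 / 0.20 = about 25 points in takers at full uptake, and 0.051 / 0.10 = about 51 points at half.

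**The case against.** The randomised intervention is a screening strategy, and Protocol, Harms describes the study as a screening trial and not a treatment trial. For that question, net harm per person assigned is a proper estimand, protected by randomisation and diluted just as the QALY effect is. This stands: the whole-arm comparison should not be displaced.

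Three stronger readings are tempting, and the documents do not support them.
- A reader might infer that the test has almost no power. That depends on rates the documents do not give. With a 2% background and full uptake, a 15-point excess has 71% to 73% pairwise power, and a 20-point excess has 88% with 475 per arm.
- A reader might take 20% as a ceiling on exposure. SAP 5.4 gives it as a planning expectation.
- A reader might infer that a null will be reported as safety. Neither document says so. What can be said is that nothing in SAP 7.1 guards against it.

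The whole-arm test is also not the only safety information. Protocol, Data Monitoring has the DSMB review adverse event reports and 18-month PHQ-8 scores, and SAP 7.2 compares mortality. Nor is lack of baseline adjustment a bias between randomised arms: it costs precision. The checklist items are not shown, so adjustment may not be possible for every harm.

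The subset has limits. With half uptake its power is only 18% to 60%. Screen-positives may have more sleep and appetite problems than the 20% or so assumed, which would lower power. Physicians notified in the Screen & Notify arm may prescribe, which narrows the contrast. Because the PHQ-8 follows randomisation, the subset also assumes that allocation does not alter the score. These points make the subset supportive evidence and make intervals more useful than p-values. They do not close the gap between the harm SAP 7.1 names and the test it plans.

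**Conclusion.** The point holds as a mismatch between question and analysis. SAP 7.1 asks about harms of drug use and answers only with an unadjusted test of whole arms, in which an excess in takers is cut to about one fifth at full uptake and one tenth at half. For a 15-point excess, whole-arm power is low over most of the assumed range (32% or less at backgrounds of 10% or more) and fair only for a rare harm with full uptake. Restricting to screen-positives raises it to 54% to 95% at full uptake. All these figures rest on assumed backgrounds, excess and uptake, and on the planned 20%.

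The firmest part is the missing interval: at 20% background, a p-value near 1 would be compatible with an excess of about 25 points in takers even if every qualifying participant took drug. It does not follow that the intention-to-treat comparison is wrong or that the trial cannot detect harm. The plan should be supplemented, not replaced.

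**What to change.** In SAP 7.1:
- Keep the whole-arm intention-to-treat comparison as the main estimate of the net harm of the screening strategy. Report it as risk differences with 95% confidence intervals at a stated time point, adjusted for the same symptom at baseline where the checklist records it.
- Add a prespecified supportive comparison of Screen, Notify & Treat with Screen & Notify among participants with PHQ-8 of 10 or more.
- Add a sensitivity comparison of all three arms among participants with baseline CES-D10 of 10 or more. This is measured before randomisation and exists in the No Screen arm, but it is not the trigger for treatment, so some dilution returns.
- State that a non-significant result will not be taken as evidence of no harm.

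In SAP 4.2 and 4.3, permit these subsets and reconcile the two sections, since one rules out analyses on a safety sample and the other is headed as defining one.

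The cost is SAP wording and a few tables from data already collected. The downsides are smaller denominators, power that stays modest if uptake is low, and sparse data for rare harms such as bleeding, where simple risk differences should be used and not a repeated-measures model.

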7.2 Mortality

Mortality will be assessed by surveying patient surrogates and through review of the electronic medical record. Group differences in mortality will be compared using chi-squared tests.

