#### **Outcomes**

Quality-adjusted Life Year Assessment (Primary). Following the precedent set by RCTs with other depressed medical populations, we chose the Short Form Health Survey (SF-12) questionnaire to assess health related quality of life for the economic analysis. The SF-12 uses Likert scales to assess health-related quality of life aspects that are most directly relevant to depressed post-ACS patients: mobility and physical activities, ability to self-care, ability to perform usual activities, pain, and anxiety/ depression. Extensive validation, including construct validity, published normative data, and sensitivity to change have all been published for this scale. It has been used extensively the cost-effectiveness of a screening or intervention practice, and has successfully been used in depression interventions with other patients, allowing comparability with other data and settings. It is ideal for using in mail or web surveys, and takes less than 5 minutes. The NICE group in Britain recommends its use for providing cost and QALY data. We will collect deaths/dates of death from the national death index & EMR.

**Depression Symptom Assessment**. The AHA advisory suggests using the PHQ-2 (yes-no version) first, and then the full PHQ-8 for the assessment of depression symptom severity. In CODIACS QoL we will not utilize the PHQ-2, and instead ask all 8 items of the PHQ-8. The PHQ-8 has excellent psychometric properties, including sensitivity to successful change from treatment, good test-retest reliability when no treatment is offered, construct validity, reasonable correlations with health-related quality of life measures, and the ability to approximate likelihood of a major depressive

disorder. Scores on the PHQ-8 range from 0- 24 and a score of ≥10 is used for detecting likely depressive disorder, and clinically significant depression levels.

**CES-D10.** The Center for Epidemiologic Studies Depression Scale (CESD) is a screening measure (NOT a diagnostic tool) developed to identify current depressive symptomatology related to major or clinical depression in adults and adolescents. The CES-D10 is a short version of the original 20-item scale. The scores range from 0 to 30, and a score of 10 or greater is considered significant.

**Depression-free Days.** These will be calculated by using linear interpolation to estimate daily depression severity from the CES-D10 obtained at each of the four assessment points for all groups.

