#### **Baseline and Follow-Up Assessments**

Research data for the study include:

- Participants' responses to self-report assessments and measures including, demographics, CES-D10, quality of life (SF-12), symptoms checklist, health service use, and lost productivity, and unanticipated events
- Electronic medical record (EMR) data extraction

There will be four study visits/interviews: baseline, and three follow-up visits/interviews, at 6-, 12, and 18-months after enrollment. The list of forms and the schedule of collection is found in **Table 1** above. Personally identifiable information (PII) and protected health information (PHI) will be collected, and will be used to contact participants for follow-up visits, treatment delivery (if applicable), and to conduct a National Death Index search within 5 years after the study ends. Only authorized personnel, who have official status as part of the authorized research team, will have access to any records containing PII and PHI.

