# **Hypothesis 1:**

Those randomized to AHA's Depression Screen, Notify & Treat intervention group will gain significantly more quality-adjusted life years across 18 months when compared to No Depression Screen control group, and also when compared to the Depression Screen & Notify control group.

We will compare outcomes for participants randomized to each of the three groups. Change in QALYs from baseline through 18 months post-randomization will serve as the primary outcome for this trial. First, quality of life utilities will be calculated using participants' scores on the SF-12 at each visit (baseline [pre-randomization] and 6, 12,

and 18 months post-randomization). All participants who complete the SF-12 will be classified according to the SF-6D. The SF-6D describes 18,000 health states. The average profile for each randomized group will be calculated. A multiple regression formula that applies weights will be used to assign quality of life utilities for each participant. Next, QALYs will be derived by multiplying the SF-6D derived quality of life utilities by 0.5 years for each 6 month-period, assuming linearity for changes in utility within each period. Any mortality events will be assigned zero QALYs from that point to the end of follow-up. With these scores calculated, we will calculate the average QALY gained (or lost) in each randomized group compared to assuming the utility calculated at baseline remained constant across 18-months.

The goal of the primary analysis is to identify whether there is difference in QALYs among the three groups. We plan to perform a two-step gate-keeping test procedure: We will first perform an F-test using ANOVA, and then proceed to do all three pairwise comparisons using two-sided t-test at 5% nominal significance *only if* the F-test has a p-value less than 0.05. With three randomization groups and three pairwise comparisons, this two-step procedure has been shown to preserve the familywise error rate in the strong sense, that is, a false positive comparison will occur at most with 5% probability under all possible scenarios.  This method is also generally more powerful than Bonferroni's adjustments.

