5.3 Primary Efficacy Analysis

Change in QALYs from baseline through 18 months post-randomization will serve as the primary outcome for this trial. QALYs were chosen as the primary outcome to facilitate comparisons of the effect of depression screening with other preventive interventions as well as to facilitate cost-effectiveness analyses and policy decisions. As QALYs do not directly assess depression, this outcome measure also minimized possible patient reporting bias as a result of lack of participant blinding or masking to condition. The goal of the primary analysis is to identify whether there is difference in the change in QALYs among the three groups. QALYs describe the duration of illness per years of survival, adjusted for quality of life experienced during that survival. One year in perfect health is equivalent to 1 QALY. All patients will complete a standardized measure of quality of life using the Short Form-12 Health Survey, Version 2™ (SF-12) at baseline, and again at 6-months, 12-months, and 18-months. 1 QALYs will be estimated from the SF-12 using the Short Form 6 Duration (SF6D) which converts data from 7 items in the SF-12 assessing 6 domains (physical functioning, role limitations, social functioning, pain, mental health and vitality) to QALYs.2 Study patients who die during the study period will be assigned a utility score of 0 for assessments after the date of death. QALYs over 18 months will be calculated as the area-under-curve by interpolating linearly the scores at the four assessments (baseline, 6-month, 12-month, 18-month). There were no data obtained or available for these measures between assessments. Change in QALYs will then be obtained by subtracting the QALYs that would have occurred if there was no change in the baseline utility score from the actual QALYs that were measured across 18 months. The analysis will follow the principle of intention-to-treat and will be conducted on each imputed dataset with the point

estimate deriving from the average of 5 datasets and the pooled variance calculated using Rubin's formula.

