5.6 Missing Data

CESD-10 questionnaire with missing data will be prorated if that participant answered more than 7 items. The missingness of data will then be assessed using Little's test. If data are found to missing at random, we will perform multivariated imputations to generate 5 imputed datasets by basing on covariates which were predictive of missing pattern such as input from prior visit and site variable; random sampling was used to impute the missing values at baseline. Missing data will be imputed sequentially, starting with the baseline visit, then the 6-month visit, followed by the 12-month and 18-month visits.

In sensitivity analyses, missing data will be handled by carrying the last observed value forward and by using best case-worst case scenario – in best case, we assumed that all missing had perfect health. In worst case scenario, we assumed all missing data had worst health status (QOL = 0).

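### Protocol and SAP name different sources for deaths, the index search has no deadline tied to the analysis, and vital status is not settled before utilities are imputed

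*SAP*

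**What the plan says.** On sources of death, the documents differ.

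- Protocol, Outcomes, in the paragraph on the primary QALY assessment: "We will collect deaths/dates of death from the national death index & EMR".
- Protocol, Baseline and Follow-Up Assessments, on the uses of identifying data: "to conduct a National Death Index search within 5 years after the study ends". Nothing ties this search to database lock or to the primary analysis.
- SAP 7.2, in the safety section: "Mortality will be assessed by surveying patient surrogates and through review of the electronic medical record". The index appears nowhere in the SAP.

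On how deaths enter the primary outcome, the documents agree in intent.

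- SAP 5.3: "Study patients who die during the study period will be assigned a utility score of 0 for assessments after the date of death". No source for that date is given.
- Protocol, Hypothesis 1: "Any mortality events will be assigned zero QALYs from that point to the end of follow-up".
- SAP 5.3, on the calculation: "QALYs over 18 months will be calculated as the area-under-curve by interpolating linearly the scores at the four assessments".

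On missing utilities, SAP 5.6 says: "If data are found to missing at random, we will perform multivariated imputations to generate 5 imputed datasets". The predictors include the prior visit and site, and "Missing data will be imputed sequentially, starting with the baseline visit". No step establishes who has died before imputation starts. The sensitivity analyses are last observation carried forward, a best case (perfect health) and a worst case (utility 0 for everything missing).

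**The concern.** The zero-utility rule works only for deaths that are known. Someone who has died and whom neither source identifies has no SF-12 at later visits, exactly like a living person who stopped responding. The main analysis then draws a utility from a model driven by earlier visits and site, so the death is scored as continued life.

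The two SAP sources could share a blind spot. Surrogate report depends on reaching someone, and the EMR comes from each site's own record systems, so a death elsewhere may not appear there. The protocol committed to a source outside those systems, but a statistician working from the SAP alone would have no reason to wait for it or use it.

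Two results are at stake: the primary QALY comparison, where the planned difference is small, and the mortality comparison in SAP 7.2, which would be undercounted. Capture might also differ by arm, since patients treated in Screen, Notify & Treat have extra specialist contact. However, only about 20% of that arm was expected to be treated, and the documents show neither the direction nor the size of any such difference.

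**Working it through.** **The plan's own scale.** SAP 5.4 gives a difference of 0.031, SD 0.17, two-sided 5%, 80% power and 475 per group.

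- n per group = 2 × (1.960 + 0.842)² × (0.17/0.031)² ≈ 473, against the stated 475. Power at 475 is 80.2%.
- 475/0.95 = 500, as stated.
- F-test power at 475 per group is 82.5% for effect size 0.18 and 83.5% for 0.031/0.17, close to the stated 84%.

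The sample size is not in dispute. The 0.031 serves only as a yardstick.

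**QALY error from one missed death.** The documents give no utility level, so let u be a constant utility while alive, and assume the imputed values also equal u. With four visits at 0, 6, 12 and 18 months, the trapezoid for a patient scored as alive throughout gives 1.5u.

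| Time of death | Utilities at the four visits | Correct area | Overstatement | u = 0.7 | u = 0.8 |
|---|---|---|---|---|---|
| Before 6 months | u, 0, 0, 0 | 0.25u | 1.25u | 0.875 | 1.00 |
| 6–12 months | u, u, 0, 0 | 0.75u | 0.75u | 0.525 | 0.60 |
| 12–18 months | u, u, u, 0 | 1.25u | 0.25u | 0.175 | 0.20 |
| Mean, equal weights (assumed) | | | 0.75u | 0.525 | 0.60 |

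The protocol's version, zero from the moment of death at time t, gives an error of u(1.5 − t). Its mean over uniform t is also 0.75u. Subtracting the baseline-constant QALYs to obtain the change leaves the error intact, because the baseline utility is the same either way.

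**Bias in an arm comparison.** Bias = (difference between arms in the proportion of missed deaths) × (mean error).

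| Net difference | Per 500 | Bias, u = 0.7 to 0.8 | Share of 0.031 |
|---|---|---|---|
| 0 | 0 | 0 | 0% |
| 0.5% | 2.5 | 0.0026 to 0.0030 | 8–10% |
| 1% | 5 | 0.0053 to 0.0060 | 17–19% |
| 2% | 10 | 0.0105 to 0.0120 | 34–39% |
| 5% (extreme bound) | 25 | 0.026 to 0.030 | 85–97% |

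The last row supposes that all 25 planned losses in one arm are missed deaths and that the other arm has none. It is a ceiling under the planned 5% loss, not a plausible case.

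**Against sampling error.** The standard error of an arm difference is 0.17 × √(2/475) = 0.011. A net three missed deaths per 500 at u = 0.7 gives 3 × 0.525/500 = 0.00315, which is about 10% of 0.031 and about 0.3 of a standard error.

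**What the sensitivity analyses do with a missed death.** Last observation carried forward scores it as alive, and the best case scores it as perfect health. The worst case scores it correctly as 0, but also assigns 0 to every living patient with missing data, so it cannot isolate the effect.

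**The case against.** A reader might infer that the SAP has withdrawn the index, and that deaths among patients who cannot be reached will therefore be imputed as alive. The documents do not support that.

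- The SAP keeps the EMR, which does not depend on contacting anyone. The protocol extracts EMR utilization data for every participant over the full 18 months (Interventions; Healthcare Utilization Data), and SAP section 8 adds claims review for utilization. Surrogates are a source that the protocol's Outcomes section does not list. Only deaths missed by both SAP sources are affected.
- The differing sentence is in the safety section. SAP 5.3 names no source, and the protocol's commitment is nowhere revoked. The SAP is silent on the index; it does not state a change.

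A reader might also infer that following the SAP gives a worse result than following the protocol. That is not shown either. If the index search came after the primary analysis, the contrast at that point would be EMR alone under the protocol against EMR plus surrogates under the SAP. If it came in time, the protocol might capture more. The documents do not settle which.

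Finally, equal misses cancel in the arm comparison, and a few net missed deaths amount to a fraction of a standard error.

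All of this stands, and it limits the point. It does not remove the conflict over sources, the open timing of the search or the missing vital-status step. Nor does cancellation in the comparison protect each arm's QALY level or the mortality count.

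**Conclusion.** The point holds in a limited form. The protocol and SAP name different death sources, the index search may come too late for the primary analysis under either document, and nothing requires vital status to be settled before imputation. A death unknown to both surrogates and EMR would be scored contrary to the SAP's own rule, in the main analysis and in the carried-forward sensitivity analysis.

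The mean error is 0.75u per missed death, resting on constant utility, imputation at that same level and equal weighting of the three intervals. The effect on the comparison depends entirely on a net imbalance between arms. Since the documents give no death rate and no capture rate for EMR or surrogates, the number of missed deaths cannot be computed, and the percentages form a sensitivity range, not an estimate. A change in the trial's conclusion is unlikely at small imbalances. This is an inexpensive improvement, not a serious flaw.

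**What to change.** 1. Reconcile the protocol's Outcomes and Baseline and Follow-Up Assessments sections with SAP 7.2. State in SAP 5.3 and 7.2 that vital status and date of death come from the National Death Index, EMR and surrogate report together.
2. Add to SAP 5.6 that vital status is settled, and the zero-utility rule applied, before any SF-12 data are imputed.
3. Run the already planned index search before database lock for participants without an 18-month assessment. If it is not available in time, prespecify a repeat of the primary and mortality analyses once it is.

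Sample size and power are unaffected. The cost is SAP wording plus either a possible wait for the linkage or one additional analysis.
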